If after at least one year of treatment, a patient achieves a complete remission (CR) or complete remission with incomplete count recovery (CRi) with MRD-negativity in the marrow, they will have the option to discontinue venetoclax. Patients with a PR with MRD-negativity will have the option of discontinuing venetoclax after 24 months of treatment. Those that come off treatment for this reason will be monitored for disease recurrence with peripheral blood MRD testing by flow cytometry approximately every 3 months. Patients who have detectable recurrence (at minimum, confirmed by two successive peripheral blood MRD positive assessments) in the peripheral blood will have the option to restart venetoclax.

In the event that patients need to restart venetoclax due to disease recurrence, they will be re-staged. If they have MRD-detectable disease but no other evidence of clinical disease progression, venetoclax can be resumed at 400 mg daily in the outpatient setting with TLS monitoring 6-8 and 24 hours after the initial dose. Patients with evidence of clinical disease progression on the re-staging evaluation will be treated with a venetoclax dose ramp up as per the label, starting with 20 mg daily and escalating to 400 mg daily. Prophylaxis against and

CONFIDENTIAL

This document is confidential. Do not disclose or use except as authorized.

treatment of TLS will be performed as during initial therapy. Patients who do not achieve MRD negativity or have disease progression after reaching full dose venetoclax monotherapy have the option to add duvelisib at the highest dose they had previously tolerated and continue it until MRD negativity is achieved on two successive peripheral blood MRD assessments or indefinitely depending on tolerability. Patients who achieve maximal response and are allo transplant candidates can elect to go off study to move on to transplant.

Participants who elect to come off therapy at the time of complete response must have received at least one year of treatment on study.

Those that discontinue duvelisib during combination therapy may continue to receive venetoclax monotherapy.

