### 5.3 Definition of Dose-Limiting Toxicity (DLT)

Dose-limiting toxicity (DLT) is based on the CTEP Active Version of the NCI Common Terminology Criteria for Adverse Events (CTCAE) Version 5.0. DLT refers to toxicities experienced at any time during the first cycle of study treatment, defined as the following:

- Grade 4 neutropenia lasting more than 5 days
- Febrile neutropenia of any duration ( $ANC < 1.0 \times 10^9/L$  and fever  $\geq 38.5^\circ F$ )
- Grade  $\geq 3$  thrombocytopenia with clinically significant bleeding
- Grade  $\geq 4$  infection by NCI-CTCAE criteria
- Any grade 3 or greater non-hematologic toxicity with the following exceptions:
  - Grade 3 or greater nausea/vomiting/diarrhea that persists for 7 days or less
  - Grade 3 asymptomatic laboratory abnormalities that improve to grade 2 or less within 3 days
- Any grade  $\geq 3$  diarrhea or vomiting or diarrhea that requires tube feeding, total parenteral nutrition, or requires or prolongs hospitalization
- Inability to receive Day 1 therapy of Cycle 2 after a delay in treatment of up to 21 days due to continued drug related toxicity from the prior cycle
- Severe cutaneous reaction (grade 3 or greater)
- Grade 4 elevation in ALT and/or AST or grade  $\geq 3$  elevation in ALT and/or AST occurring in the context of a Grade  $\geq 2$  elevation in bilirubin
- Grade 5 treatment-related adverse events

All toxicities will be considered relevant to determining DLTs and to reporting unless the event can clearly be determined to be unrelated to the study drug(s).

The DLT observation period is considered the period from the first dose of combination therapy through the completion of cycle 1. In the phase I study, if a patient comes off study due to a reason other than a DLT (e.g. disease progression) prior to the end of the DLT observation period, that patient can be replaced.

CONFIDENTIAL

This document is confidential. Do not disclose or use except as authorized.

Management and dose modifications associated with the above adverse events are outlined in Section 6.

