## **5.7 Resuming Treatment after Discontinuation**

If a patient elects to discontinue therapy and is currently in active follow up, and the participant exhibits MRD positivity at least two times in the peripheral blood or exhibits clinical disease progression in the opinion of the investigator, the participant may resume venetoclax monotherapy.

If patients do not achieve MRD negativity or has evidence of disease progression after reaching full dose venetoclax monotherapy, they have the option to add duvelisib at the highest dose they previously tolerated and continue it until MRD negativity is achieved on two successive peripheral blood MRD assessments or indefinitely depending on tolerability.

A re-staging bone marrow evaluation (aspirate, core, FISH, cytogenetics, flow/MRD, pathology) and CT scan (or PET/CT if RS) is required prior to re-initiation of venetoclax. If there is no clinical evidence of disease and only MRD detectable disease, venetoclax can be resumed at 400 mg in the outpatient setting with TLS lab monitoring 6-8 hours and 24 hours after the initial dose. If there is clinical evidence of disease, ramp up per package insert of venetoclax to the dose the participant received during their last cycle on treatment is required. The participant will have the opportunity to increase their dose of venetoclax to the MTD if tolerated after discussion with the treating investigator. Study visit frequency will coincide with where the participant left off while they were on treatment. For example, if discontinuation occurred at the end of Cycle

CONFIDENTIAL

This document is confidential. Do not disclose or use except as authorized.

37, the participant would resume a q3 month assessment schedule after the appropriate ramp up cycle

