## 6.2 Venetoclax:

The cohort doses for venetoclax in the phase I trial after intra-patient dose ramp-up are 100 mg QD (dose level +1), 200 mg (dose level +2) and 400 mg (dose level +3). If known venetoclax toxicities such as TLS, diarrhea, or neutropenia are observed, dose reductions can occur by 50% at a time to as low as 50 mg (dose level -1).

In the phase II trial, patients will ramp up to the MTD of venetoclax determined in the phase I trial. If known venetoclax toxicities such as TLS, diarrhea, or neutropenia are observed, dose reductions can occur by 50% at a time to as low as 50 mg.

Venetoclax dosing may be withheld for up to 28 days for toxicity. Doses withheld for  $>28$  days will result in discontinuation from venetoclax treatment on the study. In these cases, patients can continue with duvelisib monotherapy for up to 12 total cycles.

In cases where venetoclax has been held  $>28$  days, venetoclax may be resumed after discussion with the overall PI in cases where toxicity is thought to be due to a cause other than venetoclax. Any patient who requires  $> 3$  dose reductions for the same toxicity will be discontinued from active treatment on the study.

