## 10. STUDY CALENDAR

Baseline evaluations are to be conducted within 4 weeks (28 days) prior to patient registration with the exception of the required bone marrow biopsy, which can be done within 12 weeks (90 days) prior to registration if no significant intervening treatment has occurred since the biopsy. Treatment should begin as soon as possible after registration. In the event that the participant's condition is deteriorating, laboratory evaluations should be repeated within 48 hours prior to initiation of the next cycle of therapy.

Assessments and correlative lab draws must be performed prior to administration of any study agent. Study assessments and agents should be administered within +/- 3 days of the protocol-specified date during the dose ramp up period, +/- 7 days during the rest of the combination portion, and +/- 14 days after the completion of the combination portion (Cycle 12), unless otherwise noted.

For venetoclax ramp-up instructions, please refer to section [5.1.2](#).

If after at least one year of treatment, a patient achieves a complete remission (CR) or complete remission with incomplete count recovery (CRi) with MRD-negativity in the peripheral blood and bone marrow, they will have the option to discontinue venetoclax in favor of active disease monitoring in follow up. If after at least two years of treatment (Cycle 25 restage), a participant achieves a partial remission (PR) with MRD-negativity in the bone marrow, they will have the option to discontinue venetoclax in favor of active disease monitoring.

In the event that the participants who have discontinued treatment in favor of disease monitoring have recurrent disease as defined by MRD testing ( $>10^{-4}$ ) in at least two MRD assessments they can restart venetoclax. Patients will be treated with a dose ramp up as per the label, starting with 20 mg daily and escalating to 400 mg daily. Prophylaxis against and treatment of TLS will be performed as during initiation of venetoclax therapy. If patients do not achieve MRD negativity after reaching full dose venetoclax monotherapy, they have the option to add duvelisib at the highest dose they previously tolerated and continue it until MRD negativity is achieved on two successive peripheral blood MRD assessments or indefinitely depending on tolerability.

CONFIDENTIAL

This document is confidential. Do not disclose or use except as authorized.

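### Current sections contradict each other on restarting venetoclax and on duvelisib after grade 3 skin, liver and diarrhea events, and Table 3 does not say whether its DLT rows apply after cycle 1

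*Combined protocol and SAP*

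**What the plan says.** **Restarting venetoclax.** A patient with an MRD-negative CR or CRi may stop after at least one year of treatment (an MRD-negative PR, after two) and may restart on recurrence.

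- MRD-only recurrence, section 5 (Phase II text): "venetoclax can be resumed at 400 mg daily in the outpatient setting with TLS monitoring 6-8 and 24 hours after the initial dose".
- MRD-only recurrence, section 5.7: with "only MRD detectable disease, venetoclax can be resumed at 400 mg in the outpatient setting".
- Recurrence shown by at least two MRD assessments, introductory text of section 10: "Patients will be treated with a dose ramp up as per the label, starting with 20 mg daily and escalating to 400 mg daily".
- Clinical progression, section 5: patients are "treated with a venetoclax dose ramp up as per the label, starting with 20 mg daily and escalating to 400 mg daily".
- Clinical disease, section 5.7: "ramp up per package insert of venetoclax to the dose the participant received during their last cycle on treatment is required", with a later increase to the MTD as an option.

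**Modifying duvelisib.** Table 3 in section 6.1 covers events at least possibly related to duvelisib and sorts grade 3 events by whether they are DLTs. Sections 6.1.1 to 6.1.3 give separate rules for liver, diarrhea and skin events and draw no such distinction. Section 5.3 states that "DLT refers to toxicities experienced at any time during the first cycle of study treatment", while section 5.1.1 gives duvelisib for up to 12 cycles.

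**The concern.** All of these texts are current and operative, and none says which governs. Two sites that each follow the protocol could therefore manage the same patient differently.

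For venetoclax this is a safety matter. Section 7.3.1.1 links tumor lysis syndrome, including fatal events, to the first dose and to each dose increase. For duvelisib, the choice of text decides whether a patient continues, pauses, restarts lower or stops. That can change who is still on the drug, and at what dose, when CR is assessed at 12 months (section 13.1).

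**Working it through.** The plan states no figure on this point to reproduce. The check sets the texts side by side and then asks what scale the documents support.

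**1. Venetoclax, MRD-only recurrence.** Sections 5 and 5.7 permit 400 mg at once. Section 10 covers the same trigger and prescribes a ramp-up from 20 mg without exception. The clash runs one way: a site that ramps up breaches neither 5 nor 5.7, because both are permissive, but a site that starts at 400 mg departs from 10.

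- First dose: 400/20 = 20-fold.
- On weekly steps of 20, 50, 100, 200 and 400 mg, the first 400 mg dose falls on day 4 × 7 + 1 = 29 instead of day 1.

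**2. Venetoclax, clinical recurrence.** Section 5 escalates to 400 mg; section 5.7 goes to the last-cycle dose. Among phase II patients the targets differ only where the dose had been reduced. Section 6.2 allows that "dose reductions can occur by 50% at a time to as low as 50 mg", so the ratio runs from 400/200 = 2 to 400/50 = 8.

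**3. Duvelisib, grade 3 events.**

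| Event | Table 3, DLT row | Table 3, non-DLT row | Sections 6.1.1–6.1.3 |
|---|---|---|---|
| Skin | off active study treatment | continue | withhold, restart lower |
| First ALT/AST | withhold, restart at 25 mg daily | continue | withhold, resume same dose |
| First diarrhea | withhold, restart at 25 mg daily | continue | withhold, restart lower |
| Recurrent diarrhea | withhold, restart at 25 mg every other day | continue | discontinue |

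The only agreement is a first diarrhea event in the DLT row. Which row applies depends on section 5.3:

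- Skin: grade 3 or worse is always a listed DLT.
- Isolated ALT/AST: the liver item needs grade 4, or grade 3 or higher with raised bilirubin. An isolated grade 3 rise therefore falls under the general grade 3 item, which exempts asymptomatic laboratory changes that improve to grade 2 or less within 3 days.
- Diarrhea: episodes of 7 days or less are exempt, unless they need tube feeding or parenteral nutrition or lead to or prolong hospitalization.

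**4. Meaning of DLT in Table 3 after cycle 1.**

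- If it means meeting the 5.3 criteria at any time, the DLT-row clashes span all cycles. The clash between continuing and withholding is then limited to liver and diarrhea events that do not meet the criteria.
- If it means a DLT inside the cycle 1 window, every later grade 3 skin, liver or diarrhea event falls in the continue row, against withholding in 6.1.1 to 6.1.3.

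**5. Rough scale of the duvelisib events.** The rates are for duvelisib alone; combination rates are not given. N = 35 CLL/SLL patients, or 55 with the 20 Richter's patients.

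- Diarrhea, related, grade 3 or higher, 15.7% (section 7.4): 0.157 × 35 = 5.5; 0.157 × 55 = 8.6. Assuming 15.7% is 14/89, the exact 95% interval is 8.9% to 25.0%, or about 3 to 9 of 35. At a given rate this is an upper bound on patients affected, since it includes grade 4 and concordant events.
- ALT/AST, grade 3, 5% (section 2.4): 0.05 × 35 = 1.75; 0.05 × 55 = 2.75.
- Skin: no grade 3 rate is given. Rash is not listed among the grade 3 or higher events reaching 5% in section 7.4. As a single term it was therefore below 5%, or under 0.05 × 35 = 1.75 patients.

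**The case against.** Sections 5 and 5.7 agree on MRD-only restart, and 5.7 is the dedicated section; the outlier is introductory text to the calendar. That narrows the conflict but does not remove it, because section 10 is directive and admits no exception. The different targets for clinical recurrence are partly explained by scope: section 5 speaks for phase II, while 5.7 also covers phase I patients on lower cohort doses. A difference remains for phase II patients whose dose was reduced.

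On duvelisib, Table 3 is headed as recommended management, dose reductions are discussed with the principal investigator, and specific sections are ordinarily read over a general grid. That makes the liver and diarrhea mismatches lesser matters. It does not settle the skin conflict, because Table 3 names skin reactions itself. Section 5.2.3 requires non-hematologic toxicity to be grade 2 or lower, or at baseline, but only when a new cycle starts. It does not govern an event arising mid-cycle or the restart dose.

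Two stronger readings are tempting, and the documents do not support them.

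- A reader might infer that every grade 3 event after cycle 1 must fall in the continue row, and so for most of the planned treatment. Other text favors the criteria reading. Section 5.3 ends by sending its listed events to section 6 for management. Section 13.1 refers to meeting the DLT criteria during the first cycle, which separates criteria from window. Table 3's DLT rows run to a third occurrence, with recovery required before each restart and holds of up to 28 days allowed, which hardly fits a cycle 1 of 28 to 49 days. Section 6.1 also provides for re-increase after two or more cycles. The wording still needs to say so.
- A reader might infer that section 10's line "For venetoclax ramp-up instructions, please refer to section" 5.1.2 leads to a missing restart rule. It stands before the restart text, and the calendar's first footnote cites 5.1.2 for the cycle 1 ramp-up. It concerns initial dosing and is not a defect.

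**Conclusion.** The contradictions are real. The weightiest are the venetoclax restart (a 20-fold difference in first dose for MRD-only recurrence, and a 2- to 8-fold difference in target for dose-reduced phase II patients with clinical recurrence) and the grade 3 skin reaction (stopping study treatment against restarting lower). The ALT/AST and diarrhea mismatches alone would be table-alignment edits. The DLT label in Table 3 needs clarifying; the criteria reading is likelier, and on it the skin clash spans all cycles.

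The ratios measure the gap between the texts, not harm: the documents give neither the number of recurrences nor their tumor lysis risk. The patient counts assume that single-agent duvelisib rates carry over to the combination.

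A reader might also infer that the trial's inference is compromised. The documents do not support that. Restart arises only after at least one year of treatment and cannot alter CR at 12 months. The phase II toxicity boundary counts patients who meet DLT criteria in the first cycle, however they are managed afterwards. No sample size or error rate depends on these rules. The duvelisib conflicts can affect exposure before the 12-month assessment, by an amount that cannot be calculated from the documents.

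**What to change.** The clinical leads must reconcile the passages:

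- State one venetoclax restart rule covering MRD-only and clinical recurrence, including the ramp-up target, and have sections 5, 5.7 and 10 agree with it or cross-refer to it.
- Make Table 3 and sections 6.1.1 to 6.1.3 agree on skin, ALT/AST and diarrhea events, or state which takes precedence.
- State whether Table 3's DLT rows mean the section 5.3 criteria at any time or only within cycle 1.

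No view is given on which dose or clinical rule is right. The cost is amendment wording and a site memo, with no extra patients or analyses.

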## **5.1 Treatment Regimen**

### **5.1.1 Duvelisib:**

Duvelisib will be administered twice daily, with 28 consecutive days defined as a treatment cycle (up to 49 days for cycle 1), for up to a total of 12 cycles. Treatment will be administered on an outpatient basis with the exception of doses given while inpatient for venetoclax ramp up/dose escalation. Appropriate dose modifications are described in Section 6. Reported adverse events and potential risks are described in Section 7. No investigational or commercial agents or therapies other than those described below may be administered with the intent to treat the participant's malignancy.

### **5.1.2 Venetoclax:**

Venetoclax will be administered daily, with 28 consecutive days defined as a treatment cycle (up to 42 days for cycle 1) until the time of disease progression without clinical benefit, death, unacceptable toxicity, withdrawal of consent, or physician/patient discussion of discontinuation based on objective disease response, or they elect to go on a new CLL or Richter's directed therapy. The first dose of venetoclax will be given on day 8 of cycle 1 at a starting dose of 10 mg. All patients will be admitted for administration of the initial dose of venetoclax at each dose escalation. Patients will be started on allopurinol and IV hydration for TLS prophylaxis. TLS laboratories will be checked approximately 4, 8, 12, and 24 hours post venetoclax dose. Pre-dose laboratory values will be used as baseline to assess for potential electrolyte abnormalities following venetoclax. Patients can be discharged if no evidence of laboratory TLS 24 hours after dosing, according to the Cairo-Bishop criteria for TLS. If laboratory or clinical TLS is seen, as defined by Cairo-Bishop criteria, patients will be managed as per appendix C. Patients will be admitted weekly for each dose escalation (10 mg, 20 mg, 50 mg, 100 mg, 200 mg, 400 mg) for up to six weeks (42 days) depending on the target dose level. The same rules and TLS laboratory evaluations will be applied for each dose escalation, with the potential to escalate to 100 mg (dose level +1), 200 mg (dose level +2), and 400 mg (dose level +3).

CONFIDENTIAL

This document is confidential. Do not disclose or use except as authorized.

## **Phase II-**

Patients will undergo a dose-ramp up venetoclax as described in the phase I trial, with the exception that since there was no evidence of TLS in patients at 10 mg during phase I, participants in phase II will have the option of starting their dose ramp up at 20 mg of venetoclax for one week, followed by a weekly dose ramp-up to 400 mg daily. Patients who wish to start at 20 mg venetoclax will be required to do so inpatient for the first 2 dose ramp-ups (at 20 mg and 50 mg) and can then do the remaining ramp-ups (i.e. to 100, 200, and 400 mg) as an outpatient.

Patients who are low- or medium risk for TLS and wish to be treated all in the outpatient setting will have to start at 10 mg and then the following week go up to 20 mg, and then complete the rest of the usual ramp-up to 50 mg, 100 mg, 200 mg, and 400 mg.

High risk patients will be hospitalized for the initial dose ramp-ups, but will have the option to start at 10 or 20 mg. If they start at 10 mg then they will need to be hospitalized for the first 3 dose ramp-ups (10 mg, 20 mg, and 50 mg), or for the first two dose ramp ups (20mg and 50mg) if they start at 20 mg.

### **Inpatient:**

When venetoclax dosing is performed as an inpatient, TLS labs must be performed STAT at least at the following time points: pre-dose (within 4 hours before venetoclax administration), and approximately 4, 8, 12, and 24 hours after the first dose of venetoclax and each subsequent dose escalation. Pre-dose laboratory values will be collected and used as baseline to assess potential electrolyte abnormalities occurring post venetoclax administration.

### **Outpatient:**

When venetoclax dosing is performed as an outpatient, TLS labs should be checked pre-dose, approximately 6-8 hours after first dose and approximately 24 hours after treatment.

**Accelerated ramp up for RS patients:** Given the potential for rapidly progressive RS, these RS patients will also have the option to undergo an accelerated venetoclax ramp-up in the inpatient setting modeled after another study of venetoclax plus chemotherapy that was recently reported ([name] et al., ICML, 2019). In that study, venetoclax was safely ramped up in a daily fashion for 20 RS patients, who were monitored closely in the inpatient setting, with no evidence of tumor lysis syndrome. The venetoclax is dosed at 20 mg for day 1, and if no TLS is observed on labs done 6-8 hours and 24 hours later, then the dose is ramped up to 50 mg on day 2, 100 mg on day 3, 200 mg on day 4, and 400 mg on day 5 if the daily labs done 6-8 hours and 24 hours later continue to show no TLS. If laboratory TLS does occur, the next day's dose will be held until there is improvement in the TLS, at which point escalation to the next dose may occur

Subjects should take venetoclax within approximately 30 minutes after the completion of breakfast or the subject's first meal of the day. Subjects may not consume: grapefruit or grapefruit products, Seville oranges (including marmalade containing Seville oranges) or

CONFIDENTIAL

This document is confidential. Do not disclose or use except as authorized.

starfruit within the 3-day period prior to the first study drug administration and until the last day of treatment is completed due to possible CYP3A mediated metabolic interaction.

The participant will maintain a medication diary of each dose of medication. The medication diary should be returned to clinic staff at the end of each cycle or visit period (every 2, 3 or 6 cycles as outlined in the study calendar). If the patient has not taken their duvelisib dose within 4 hours and venetoclax dose within 8 hours of the recommended time, they will be instructed to skip their dose.

Administration of venetoclax and duvelisib may be in any order.

